4 STUDY VARIABLES AND COVARIATES

4.1 PRIMARY VARIABLE

The primary variable for statistical comparison between treatment groups will be the incidence of treatment-emergent adverse events in the ABX464 treated Patients versus placebo, categorized by severity.

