11.3 EFFICACY ANALYSES

Analysis of efficacy data will be carried out on Efficacy Set 1 and will be repeated for Efficacy Set 2. Treatment comparisons will be ABX464 in two different doses vs. placebo.

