11.3.1 Primary Variable

The primary efficacy endpoint of the study, the ACR20 response rate, will be compared in subjects who received a given dose of ABX464 or placebo by likelihood ratio chi-square test on a 10% two-sided level (Table 14.2.1.1 and Table 14.2.1.2).

The result of the test will be interpreted in a descriptive manner therefore no adjustment for multiple comparison is applied.

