11.3.2 Secondary Variables

Descriptive statistics will be presented by treatment arm for all secondary efficacy variables for each measurement timepoints separately for the study groups:

- Proportion of patients achieving a categorical ACR20 response at Week 12 (Table 14.2.2.1 and Table 14.2.2.2).
- Change from Baseline in the individual components of the ACR20 response at Week 2, Week 4, Week 8 and Week 12 (Table 14.2.3.1 and Table 14.2.3.2):
 - C-Reactive Protein (CRP) (mg/L),
 - Tender/painful joint count (TJC) (28 joints),
 - Swollen joint count (SJC) (28 joints),
 - Patient assessment of joint pain (Pain-VAS),
 - Patient global assessment of disease (PtGA),
 - Physician's Global Assessment of Disease (PrGA),
 - HAQ-DI.
- Change from Baseline in the following disease parameters at Week 2, Week 4, Week 8 and Week 12:
 - ESR (Table 14.2.4.1.1 and Table 14.2.4.1.2);
 - DAS28-CRP (Table 14.2.4.2.1 and Table 14.2.4.2.2) and DAS28-ESR (Table 14.2.4.3.1 and Table 14.2.4.3.2);
 - SDAI score (Table 14.2.4.4.1 and Table 14.2.4.4.2);
 - CDAI score (Table 14.2.4.5.1 and Table 14.2.4.5.2);
 - FACIT-Fatigue score (Table 14.2.4.6.1 and Table 14.2.4.6.2).
- Proportion of patients achieving:
 - ACR20/50/70 response;
 - Categorical DAS28-CRP response;
 - LDA;
 - DAS28-ESR remission;
 - ACR/EULAR remission;
 - SDAI remission;
 - CDAI remission
 at Week 2, Week 4, Week 8 and Week 12 (Table 14.2.5.1 and Table 14.2.5.2).

These statistics include:

- Continuous variables: mean, standard deviation, minimum and maximum, stratified 95% confidence intervals, median and quartiles will be presented.
- Categorical variables: counts, rates and stratified 95% confidence intervals for the rates will be calculated.

In addition to descriptive statistics, mixed model analysis of covariance will be conducted for the following measurements:

- The change from baseline in DAS28-CRP and DAS28-ESR;
- The change from baseline in the individual components of the ACR20 response (CRP, TJC(28), SJC(28), Pain-VAS, PtGA, PrGA, HAQ-DI) and in ESR;
- The change from baseline in SDAI and CDAI scores.

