11.6 SAFETY ANALYSES

11.6.1 Adverse Events

An overall summary table will be presented (any adverse event, any treatment emergent adverse event (TEAE), any serious adverse event (SAE), death, any grade 3 or higher adverse events from baseline to the end of Study) (*Table 14.3.1.1*). This analysis will be conducted on SAF population.

Primary safety endpoint, the rate of all treatment emergent adverse experiences, will be compared in subjects who received a given dose of ABX464 or placebo by likelihood ratio chi-square test on a 10% two-sided significance level (*14.3.1.2.1*).

Two periods will be defined for TEAE:

- Period I: any adverse event which occurs or worsens from first dosing to Day 84;
- Period II: any adverse event which occurs after Day 84.

Adverse events will be described by primary system organ class and preferred term according to the two periods. Numbers and percentage of patients, and number of occurrences of adverse event will be presented for:

- TEAE (Table 14.3.1.2.2 and Table Table 14.3.1.2.3);
- Serious TEAE (Table 14.3.1.3.1 and Table Table 14.3.1.3.2);
- TEAE leading to drug discontinuation (Table 14.3.1.4.1 and Table Table 14.3.1.4.2);
- TEAE of grade 3 or 4 (Table 14.3.1.5.1 and Table Table 14.3.1.5.2);

Further assessment of safety will be based on the frequency of adverse events (with and without regard to causality) graded according to the CTC-AE Classification and also, the review of individual values for clinical laboratory data, vital signs and ECG focusing on the detection of abnormal values and PCSAs [potentially clinically significant abnormalities (PCSAs) determined upon investigator considerations].

Adverse events will be tabulated (counts and percentages) by group. All adverse events will be listed, and the data will be tabulated by body system/organ class. Adverse event tabulations will include all treatment emergent adverse events, which will be further classified by severity, and relationship to treatment and dose level.

All adverse events (AE) will be classified using the version of the MedDRA coding dictionary specified in the DHM.

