15 SHELLS FOR TABLES, FIGURES AND LISTINGS

The intended layouts for tables, figures and listings are presented. However, it may be appropriate for the Orion programmer to change the layouts, upon review of the data available, for completeness and clarity.

QCd output will be produced as Rich Text Format (.rtf) files for convenient inclusion in the CSR.

Subject to this, the following will apply:

- Layout will be landscape, fixed width, font size 8.
- Each output will have the heading:
ABX464-301 (left); date ddMMMyyyy (right)
- Table headings will define the analysis set used for the summary/analysis.
- All outputs will have a footer specifying the SAS program path and filename (left); page x/y (right)
- Tables will have a footer specifying the source listing
- Figures will have a footer specifying the source table or listing
- Additional footnotes will be included where appropriate for clarification.
- Treatment group and patient number and will be included in all listings.

ABX464-301

ddMMMyyyy

Table 14.1.1 Screening Failures (All Enrolled Patients)

	Total Enrolled (N=xx)
Total number of enrolled patients	xx
Screened	xx (xx.x%)
Randomised	xx (xx.x%)
Screening failure	xx (xx.x%)
Baseline failure	Xx (xx.x%)
Primary Reason for screening failure	
Inclusion criterion not met	xx (xx.x%)
Exclusion criterion	xx (xx.x%)
Withdrawal by patient	xx (xx.x%)
Etc	

The denominator for each percentage is the number of enrolled patients.

Source: Listing 16.2.1.1 and 16.2.1.2
Path\Filename

Page x/y

ABX464-301

ddMMMyyyy

Table 14.1.2 Patient Disposition (All Randomised Patients)

	ABX-464 100mg (N=xx)	ABX-464 50mg (N=xx)	Placebo (N=xx)	Total (N=xx)
Full Analysis Set	xx (xx.x%)	xx (xx.x%)	xx (xx.x%)	xx (xx.x%)
Safety Set	xx (xx.x%)	xx (xx.x%)	xx (xx.x%)	xx (xx.x%)
Efficacy Set 1	xx (xx.x%)	xx (xx.x%)	xx (xx.x%)	xx (xx.x%)
Efficacy Set 2	xx (xx.x%)	xx (xx.x%)	xx (xx.x%)	xx (xx.x%)
Per Protocol Set	xx (xx.x%)	xx (xx.x%)	xx (xx.x%)	xx (xx.x%)

The denominator for each percentage is the number of randomized patients in the column.

Source: Listing 16.2.1.1 and 16.2.1.2
Path\Filename

Page x/y

ABX464-301

ddMMMyyyy

Table 14.1.3 Study Termination and Primary Reason for Withdrawal (All Randomised Patients)

	ABX-464 100mg (N=xx)	ABX-464 50mg (N=xx)	Placebo (N=xx)	Total (N=xx)
Randomised	xx	xx	xx	xx
Completed	xx (xx.x%)	xx (xx.x%)	xx (xx.x%)	xx (xx.x%)
Early withdrawal	xx (xx.x%)	xx (xx.x%)	xx (xx.x%)	xx (xx.x%)
Main reason for early withdrawal				

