The denominator for each percentage is the number of patients within the column.
Medical history refers to conditions which stopped prior to or at the screening visit.

Source: Listing 16.4.4
Path\Filename

Page x/y

*This layout also applies to:
Table 14.1.5.2 Current Medical Conditions (Full Analysis Set) [Programmer's Note: Update footnote to medical conditions definition.]*

ABX464-301

ddMMMyyyy

Table 14.2.1.1 Analysis of ACR20 Response Rate (Efficacy Set 1)

		ABX-464 100mg (N=xx)	ABX-464 50mg (N=xx)	Placebo (N=xx)	p-value
ACR20 Response	N	xx	xx	xx	
	Yes	xx (xx.x%)	xx (xx.x%)	xx (xx.x%)	
	No	xx (xx.x%)	xx (xx.x%)	xx (xx.x%)	
Chi-squared test					x.xxxx

Response rate between treatments is compared using likelihood ratio chi-square test at a two-sided 10% significance level.

Source: Listing 16.2.6
Path\Filename

Page x/y

This layout also applies to:
Table 14.2.1.2 Analysis of ACR20 Response Rate (Efficacy Set 2)
Table 14.2.1.3 Analysis of ACR20 Response Rate (PP Set)

ABX464-301

ddMMMyyyy

Table 14.2.2.1 Summary of Categorical ACR20 Response at Week 12 (Efficacy Set 1)

		ABX-464 100mg (N=xx)	ABX-464 50mg (N=xx)	Placebo (N=xx)
Week 12	N	xx	xx	xx
	Rate	xx.x %	xx.x %	xx.x %
	Stratified 95% CI	xx.x % - xx.x %	xx.x % - xx.x %	xx.x % - xx.x %

Source: Listing 16.2.6
Path\Filename

Page x/y

This layout also applies to:
Table 14.2.2.2 Summary of Categorical ACR20 Response at Week 12 (Efficacy Set 2)

ABX464-301

ddMMMyyyy

Table 14.2.3.1 Analysis of the individual components of the ACR20 response (Efficacy Set 1)

		ABX-464 100mg (N=xx)	ABX-464 50mg (N=xx)	Placebo (N=xx)	p-value
CRP					
Baseline	N	xx (xx.x %)	xx (xx.x %)	xx (xx.x %)	
	Mean	xx.xx	xx.xx	xx.xx	
	Stratified 95% CI	xx.xx - xx.xx	xx.xx - xx.xx	xx.xx - xx.xx	
	SD	xx.xx	xx.xx	xx.xx	
	Minimum	xx.x	xx.x	xx.x	
	Maximum	xx.x	xx.x	xx.x	
	Median	xx.xx	xx.xx	xx.xx	
	Quartiles	xx.xx - xx.xx	xx.xx - xx.xx	xx.xx - xx.xx	
Week 2	N	xx (xx.x %)	xx (xx.x %)	xx (xx.x %)	
	Mean	xx.xx	xx.xx	xx.xx	
	Etc				
Change from baseline to Week 2	N	xx (xx.x %)	xx (xx.x %)	xx (xx.x %)	
	Mean	xx.xx	xx.xx	xx.xx	
	Etc				
Analysis of Covariance (change from baseline to Week 2)					x.xxxx
Week 4	N	xx (xx.x %)	xx (xx.x %)	xx (xx.x %)	
	Mean	xx.xx	xx.xx	xx.xx	
	Etc				
Etc					

Etc

Mixed model analysis of covariance is conducted for the changes of baseline for each parameter.

Source: Listing 16.4.5.1
Path\Filename

Page x/y

Programmer's Note: List of variables consists of CRP, TJC, SJC, Pain-VAS, PtGA, PrGA, HAQ-DI.

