Table 14.2.5.1 Summary of Patients Achieving Different Responses and Remissions (Efficacy Set 1)

		ABX-464 100mg (N=xx)	ABX-464 50mg (N=xx)	Placebo (N=xx)
ARC20 Response				
Week 2	N	xx	xx	xx
	Rate	xx.x %	xx.x %	xx.x %
	Stratified 95% CI	xx.x % - xx.x %	xx.x % - xx.x %	xx.x % - xx.x %
Week 4	N	xx	xx	xx
	Rate	xx.x %	xx.x %	xx.x %
	Stratified 95% CI	xx.x % - xx.x %	xx.x % - xx.x %	xx.x % - xx.x %
Etc				
Etc				

Source: Listing 16.4.5.3
Path\Filename

Page x/y

Programmer's Note: List of variables consists of ACR20/50/70 response, Categorical DAS28-CRP response, LDA, DAS28-ESR remission, ACR/EULAR remission, SDAI remission, CDAI remission.

This layout also applies to:

Table 14.2.5.2 Summary of Patients Achieving Different Responses and Remissions (Efficacy Set 2)

ABX464-301

ddMMMyyyy

Table 14.3.1.1 Summary of Adverse Events (Safety Set)

	ABX-464 100mg (N=xx)		ABX-464 50mg (N=xx)		Placebo (N=xx)		Total (N=xx)	
	n	N (%)	n	N (%)	n	N (%)	n	N (%)
Any Adverse Event	xx	xx (xx.x%)	xx	xx (xx.x%)	xx	xx (xx.x%)	xx	xx (xx.x%)
Any Treatment-Emergent Adverse Event	xx	xx (xx.x%)	xx	xx (xx.x%)	xx	xx (xx.x%)	xx	xx (xx.x%)
Any Serious Adverse Event	xx	xx (xx.x%)	xx	xx (xx.x%)	xx	xx (xx.x%)	xx	xx (xx.x%)
Adverse Event leading to death	xx	xx (xx.x%)	xx	xx (xx.x%)	xx	xx (xx.x%)	xx	xx (xx.x%)
Any grade 3 or higher Adverse Event	xx	xx (xx.x%)	xx	xx (xx.x%)	xx	xx (xx.x%)	xx	xx (xx.x%)

The table presents number of events (n) and number and percentage of patients (N(%)).
The denominator for each percentage is the number of patients within the column.

Source: Listing 16.2.7
Path\Filename

Page x/y

ABX464-301

ddMMMyyyy

Table 14.3.1.2.1 Analysis of Treatment-Emergent Adverse Events (Safety Set)

		ABX-464 100mg (N=xx)	ABX-464 50mg (N=xx)	Placebo (N=xx)	p-value
Any Treatment-Emergent Adverse Event	N	xx	xx	xx	
	Yes	xx (xx.x%)	xx (xx.x%)	xx (xx.x%)	
	No	xx (xx.x%)	xx (xx.x%)	xx (xx.x%)	
Chi-squared test					x.xxxx

The denominator for each percentage is the number of patients within the column
TEAE rate between treatments is compared using likelihood ratio chi-square test at a two-sided 10% significance level.

Source: Listing 16.2.7
Path\Filename

Page x/y

ABX464-301

ddMMMyyyy

Table 14.3.1.2.2 Treatment-Emergent Adverse Events, by SOC and PT: Period 1 (Safety Set)

	ABX-464 100mg (N=xx)			ABX-464 100mg (N=xx)			Placebo (N=xx)			Total (N=xx)		
	n	N (%)	duration (days)	n	N (%)	duration (days)	n	N (%)	duration (days)	n	N (%)	duration (days)

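### The ACR20 and any-TEAE table shells carry one p-value for three arms where the text compares each dose with placebo, and no dose-minus-placebo difference with an interval is planned

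*SAP*

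**What the plan says.** The method text is pairwise throughout. For efficacy, SAP 11.3 states "Treatment comparisons will be ABX464 in two different doses vs. placebo", and SAP 11.3.1 compares ACR20 "by likelihood ratio chi-square test on a 10% two-sided level" between a given dose and placebo. SAP 11.6.1 uses the same test for TEAEs, comparing patients on a "given dose of ABX464 or placebo by likelihood ratio chi-square test on a 10% two-sided significance level". SAP 3.5 sizes the trial for one active group against placebo: 84% power for ACR20 at 0.65 v 0.25, and 89% for TEAE rates of 10% v 50%.

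The shells in SAP 15 look different. Table 14.2.1.1 (layout reused for 14.2.1.2 and 14.2.1.3) and Table 14.3.1.2.1 each have three arm columns, one chi-squared row and one p-value cell. Their footnotes read "Response rate between treatments is compared using likelihood ratio chi-square test at a two-sided 10% significance level" and "TEAE rate between treatments is compared using likelihood ratio chi-square test at a two-sided 10% significance level". SAP 10.1 says the shells define the format of the summaries. SAP 15 adds that "it may be appropriate for the Orion programmer to change the layouts", which permits a second p-value but does not require one.

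On estimates, SAP 11.3.2 plans per-arm intervals for categorical efficacy variables: "stratified 95% confidence intervals for the rates will be calculated". SAP 4.1 says "The primary variable for statistical comparison between treatment groups will be the incidence of treatment-emergent adverse events", categorised by severity. SAP 11.6.1 tests the rate of all TEAEs, and its table gives counts, percentages and a p-value. The confidence interval clause in SAP 10.1 stands in the paragraph on continuous variables.

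Randomisation is stratified by previous anti-TNF exposure (SAP 3.6 and 10.2). The stratum enters the mixed models and the per-arm efficacy intervals in SAP 11.3.2, but neither chi-square test.

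**The concern.** A programmer who follows the shells could run a three-arm test on 2 degrees of freedom. That asks whether any arm differs from any other, not whether a given dose differs from placebo, and it can point the other way from the pairwise tests.

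SAP 10.6 and 11.3.1 say the results are interpreted descriptively. A descriptive reading needs the size of each dose-versus-placebo difference and its precision, and the plan provides neither directly. With 20 patients per arm a p-value alone says little. A safety comparison with p = 0.20 may be taken as reassurance when the data are compatible with a large excess.

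The ACR20 test also sets aside the one factor on which randomisation was stratified, although the other efficacy analyses use it.

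**Working it through.** **Inputs.** From SAP 3.5: 20 per arm, 10% two-sided, ACR20 0.65 v 0.25, TEAE 0.50 v 0.10. Example counts, the 0.45 rate, stratum splits and stratum odds ratios are assumptions; the documents do not give them.

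**1. The plan's own power figures.** Pooled normal approximation: power = Φ{[d − 1.645√(2p̄(1−p̄)/20)] / √([p1(1−p1)+p2(1−p2)]/20)}.
- ACR20: (0.40 − 1.645 × 0.1573)/0.1440 = 0.98, so 83.7% (stated 84%). Exact enumeration of the likelihood ratio (LR) test gives 83.3%.
- TEAE: (0.40 − 1.645 × 0.1449)/0.1304 = 1.24, so 89.2% (stated 89%). Exact LR gives 91.2%.

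The stated figures therefore belong to pairwise 1-df tests.

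**2. Where the two readings part.** G = 2ΣO ln(O/E), referred to chi-square on 2 df (three arms) or 1 df (one dose v placebo). On 2 df, p = exp(−G/2).

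For 13/20, 5/20 and 9/20, each arm expects 9 events and 11 non-events. G = 2[13 ln(13/9) + 7 ln(7/11) + 5 ln(5/9) + 15 ln(15/11)] = 6.66, so p = 0.036. The placebo terms are zero.

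| 100 mg, 50 mg, placebo (of 20) | 2-df p | 100 mg v placebo | 50 mg v placebo |
|---|---|---|---|
| 13, 5, 9 | 0.036 | 0.20 | 0.18 |
| 14, 10, 8 | 0.147 | 0.054 | 0.52 |

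**3. ACR20 power of a 2-df test.** Exact enumeration at critical value 4.605, against 83.3% for the pairwise test.

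| Rates (100 mg, 50 mg, placebo) | 2-df power |
|---|---|
| 0.65, 0.65, 0.25 | 86.9% |
| 0.65, 0.25, 0.25 | 86.6% |
| 0.65, 0.45 (assumed), 0.25 | 76.6% |

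The share of trials significant on 2 df with neither dose significant against placebo is 0.02% at 0.65, 0.65, 0.25. It reaches 11.6% only at an assumed 0.65, 0.25, 0.45, where 50 mg does worse than placebo.

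**4. What an interval adds.** TEAEs in 12/20 v 8/20 give a difference of 20 points and LR p = 0.20. The 90% score interval runs from −6 to +44 points.

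**5. Stratifying the ACR20 test.** Exact power of the uncorrected Cochran-Mantel-Haenszel (CMH) test v LR, with overall rates held at 0.65 and 0.25.

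| Assumed stratum odds ratio | Split 10/10: CMH v LR | Split 14/6 | Split 6/14 |
|---|---|---|---|
| 1 | 82.3% v 83.3% | 82.0% v 83.3% | 82.0% v 83.3% |
| 2 | 83.6% v 83.5% | 83.0% v 83.5% | 83.1% v 83.5% |
| 4 | 87.1% v 84.2% | 85.8% v 84.1% | 85.8% v 84.0% |
| 8 | 90.5% v 85.2% | 89.2% v 85.1% | 88.9% v 84.8% |

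The loss is 1.0 to 1.3 points at odds ratio 1. The gain is 1.7 to 2.9 points at 4 and 4.1 to 5.3 points at 8.

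**6. Side note on the LR test for TEAEs.** At 20 v 20 its exact size is 17.3% at a 10% rate in both arms, with a peak of 20.2% at 6.5%. It exceeds 12% from 3% to 15.5%, and the pattern is mirrored above 50%. From 20% to 80% it is 9.5 to 11.9%, including assumed 22 v 20 and 18 v 20 layouts.

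**The case against.** The strongest reply is that the method is already right. SAP 11.3, 11.3.1, 11.6.1 and 3.5, and protocol 8.2, 8.4 and 8.6, all describe a dose against placebo, and a careful programmer may recover that intent. This stands: the first limb is a conflict between text and shell, corrected by one more cell. A reader might infer that the plan specifies a three-arm test, or that such a test would cost power. The text does not specify one, and at the plan's own rates of 0.65 and 0.25 the 2-df test has more power than the pairwise test. The trouble is that it answers a different question.

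Second, counts and denominators will be reported, so a reader can derive differences and unstratified intervals. That is true, and ACR20 does have per-arm intervals, so it would be wrong to say ACR20 has none. But a post hoc interval by an unnamed method is weaker than a planned one, and the any-TEAE rate has no planned interval.

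Third, a reader might infer that leaving out the stratum inflates the error rate. It does not, and no document says that prior anti-TNF exposure is prognostic. The gain is conditional, and for TEAEs there is no stated reason to expect one.

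Fourth, the LR test might be said to miss its 10% level for TEAEs. That matters only if the rate is below about 15% or above about 85%. The 10% in SAP 3.5 is the lower rate of a power scenario, not an expected rate. Protocol 7 (disease progression reported as an adverse event) and SAP 11.6.1 (events of unclear timing counted as treatment-emergent) point to a higher one.

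**Conclusion.** The point holds in three parts of unequal weight.

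- **Text against shell.** Certain from the documents, and able to change a reported result, as the two examples in the working show. How often it would do so depends on the true rates.
- **No planned difference with an interval.** Certain for both endpoints, and most important for the any-TEAE comparison. At 12/20 v 8/20 a p-value of 0.20 would hide an interval reaching +44 points.
- **Stratum unused in the ACR20 test.** A modest efficiency point, not a validity problem. The power changes rest on assumed splits and odds ratios.

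The documents do not support a claim that the stated power is wrong, that the plan calls for an omnibus test, or that the TEAE test must be replaced. The changes should be made while the SAP can still be amended without knowledge of treatment codes; SAP 1.1 says it is to be finalised before unblinding.

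**What to change.** 1. In Tables 14.2.1.1 to 14.2.1.3 and 14.3.1.2.1, show one p-value for 100 mg v placebo and one for 50 mg v placebo, and reword the footnotes to match.
2. In SAP 11.3.1 and 11.6.1 and the same shells, add the risk difference beside each p-value, with a confidence interval by a named method. The Miettinen-Nurminen score interval at 90% is a suitable choice alongside the 10% test.
3. For ACR20, use the uncorrected CMH test stratified by prior anti-TNF exposure and the stratified Miettinen-Nurminen interval with Mantel-Haenszel weights. Over all outcomes in four assumed layouts, this interval excluded zero exactly when the CMH p-value was below 10%. Record the change in SAP 1.2, because protocol 8.2 names the LR test.
4. For TEAEs, the LR test may stay. Label the unstratified interval as descriptive, because it need not agree with the LR test at the margin. At 10/20 v 5/20 the LR p-value is 0.09998, just below 10%. The Pearson statistic is 40 × (10×15 − 10×5)²/(20×20×15×25) = 2.67, short of 2.706, so the score interval includes zero.

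The cost is SAP wording, four table shells, one line in SAP 1.2, and about 1 point of ACR20 power if the stratum is not prognostic. No new data are needed.

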8.4. Safety Analyses

Adverse events will be coded using the standard dictionary (MedDRA) down to the lower level term (LLT).

An overall summary table will be presented (Any adverse event, any treatment emergent adverse event (TEAE), any serious adverse event (SAE), death, any grade 3 or higher adverse events from baseline to the end of Study. This analysis will be conducted on SAF population.

Two periods will be defined for TEAE:

- Any adverse event which occurs or worsens from first dosing to Day 84;
- Any adverse event which occurs after Day 84.

Adverse events will be described by primary system organ class and preferred term. Numbers and percentage of patients, and number of occurrences of adverse event will be presented for:

- TEAE;
- Serious TEAE;
- TEAE leading to drug discontinuation;
- TEAE of grade 3 or 4;
- TEAE for which relationship with the study drug is recorded as possible or probable.

Analysis of safety will be performed on the safety data set consisting all subjects who received at least one dose of ABX464 in the study.

Primary safety endpoint, the rate of all treatment emergent adverse experiences, will be compared in subjects who received a given dose of ABX464 or placebo by likelihood ratio chi-square test on a 10% two-sided significance level.

Further assessment of safety will be based on the frequency of adverse events (with and without regard to causality) graded according to the CTC-AE Classification and also, the review of individual values for clinical laboratory data, vital signs and ECG focusing on the detection of abnormal values and PCSAs [potentially clinically significant abnormalities (PCSAs) determined upon investigator considerations].

Adverse events will be tabulated (counts and percentages) by group. All adverse events will be listed, and the data will be tabulated by body system/organ class. Adverse event tabulations will include all treatment emergent adverse events, which will be further classified by severity, and relationship to treatment and dose level.

Clinical laboratory parameters, vital signs, ECG will be summarized by using descriptive statistics (n, mean, SD, SEM, median, minimum and maximum). Number of patients with at least one abnormal value will be tabulated (counts and percentages) for each parameter in summary shift tables, by group and dose.

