Patient line plots will use actual time on the time axis. Mean plots will use a linear time scale for the nominal times of the visits and will be labelled by visit. Results from an early withdrawal visit will be excluded.

If changes in severity for the same TEAE have been reported separately but with the same AE number, they will be collapsed to a single AE with maximum severity for the summary tables, but listed as reported.

Classifications of medical history, concomitant medication and adverse events will be sorted alphabetically within the summary tables.

If any laboratory assessments are repeated at the same visit, the result from the repeat assessment will be used in summaries. Both values will be listed.

CRF data collected/ Data collected on the eCRF will be presented within data listings. The data listings will be sorted by treatment group, country, centre number, patient number and visit/week/day. Treatment group will be as allocated (randomised). If any patients receive the wrong treatment this will be flagged in all listings. Visits outside the visit windows will be identified within the listings. For patients who complete the study, the last visit will be described in the listings as '<Day X>'; for those who withdraw early it will be described as 'End of Study'.

The date format for all output presentations will be 'ddMMMyyyy'.

All statistical analysis will be performed using SAS 9.2 or higher.

All hypothesis testing will be carried out at the 5% (2-sided) significance level unless stated otherwise.

P-values will be rounded to four decimal places. P-values less than 0.0001 will be reported as <0.0001 in tables.

If any of the assumptions underlying the formal statistical methods proposed are violated during the analysis of the final data, alternative statistical methods will be used and any changes documented in the statistical methods section of the clinical study report (CSR), including the rationale for use.

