Events will be classified as treatment-emergent if they started or increased in severity on or after the first date and time of medication dosing at Visit 1 and up to study closure or withdrawal date. If an event start date is partial, then the start day, month, year or stop date will be used to determine if the event is treatment-emergent. If the classification of the AE cannot be determined from the data available, then the event will be considered treatment-emergent.

Treatment-emergent adverse events (TEAEs) will be further classified as follows:

Severe TEAEs: Severity classified as 'severe' (Common Toxicity Criteria [CTC] grade 3 or 4) or missing.

Serious TEAEs: Serious classified as 'yes' or missing.

Drug-related TEAEs: Relationship to study drug classified as 'related' or missing.

Serious drug-related TEAEs: Both serious and drug-related, as specified above.

TEAEs leading to withdrawal from study: Action taken classified as 'discontinued'.

All AE summary tables will show the number (%) of patients having at least one event and the number of events in each treatment group and overall. Median duration of AEs (from baseline to occurrence) will be presented in the tables. Note: If a patient has multiple AEs with the same preferred term, these will be summarised once within the count for N (%) of patients, but each event will be counted within the number of reports n of each AE. Changes in severity of the same AE (if collected) will be counted only once within the number of reports n of each AE.

The following will be presented in listing format within the data summaries:

- Deaths (Table 14.3.2.1);

- Serious Adverse Events (*Table 14.3.2.2*);
- Adverse Events which Led to Withdrawal (*Table 14.3.2.3*).

All adverse events (including non-treatment-emergent events) recorded on the CRF will be listed within the data listings.

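### Period II of the TEAE split leaves out worsening, so an event that starts by Day 84 and first reaches grade 3 later is tabulated as a Period 1 grade 3-4 event

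*SAP*

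**What the plan says.** SAP 11.6.1 splits treatment-emergent events at Day 84:

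- "Period I: any adverse event which occurs or worsens from first dosing to Day 84"
- "Period II: any adverse event which occurs after Day 84"

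Protocol 8.4 words its second period in the same way: "Any adverse event which occurs after Day 84".

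The TEAE definition in SAP 11.6.1 is wider. "Events will be classified as treatment-emergent if they started or increased in severity on or after the first date and time of medication dosing", with a window that runs "up to study closure or withdrawal date". Worsening after Day 84 therefore makes an event treatment-emergent.

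For severity changes reported separately under one AE number, SAP 10.1 says that "they will be collapsed to a single AE with maximum severity for the summary tables, but listed as reported". SAP 11.6.1 adds that such changes, if collected, add only one to the number of reports of that AE.

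Four families of tables are produced once per period: all TEAEs, serious TEAEs, TEAEs leading to drug discontinuation, and TEAEs of grade 3 or 4 (Tables 14.3.1.5.1 and 14.3.1.5.2). No section says to which period a grade reached after Day 84 belongs, or asks for a maximum within a period.

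**The concern.** Two rules interact badly. The first period accepts both onset and worsening; the second accepts onset only. The collapse rule then attaches the highest grade on the whole record to the event, whenever that grade was reached. A grade first reached after Day 84 can thus be reported as severity of the period before it, while the period in which it was reached shows nothing.

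The primary endpoint is TEAE incidence categorized by severity (Protocol 2.3, SAP 4.1). The table that carries the test (14.3.1.2.1) is any TEAE, yes or no, and Table 14.3.1.1 has one row for grade 3 or higher among adverse events generally. In the SAP's table list, the grade 3-4 pair by period are the only tables given over to TEAE severity, and they are the ones mainly affected. At stake is whether a reader of that pair can tell when severe events arose.

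**Working it through.** The plan gives no figure on this point, so the check applies the written rules to constructed records.

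**Rules used**

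1. TEAE: onset or increase in severity from first dose to study closure or withdrawal (SAP 11.6.1).
2. Period I: onset or worsening from first dose to Day 84. Period II: onset after Day 84 (SAP 11.6.1, Protocol 8.4).
3. Grade in summary tables: the maximum over all records with the same AE number (SAP 10.1).
4. Table 14.3.1.5.1 takes Period I events of grade 3 or 4; Table 14.3.1.5.2 takes Period II events of grade 3 or 4.

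**Result as written** (each record under one AE number)

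| Record | TEAE | Period I | Period II | Grade | 14.3.1.5.1 | 14.3.1.5.2 |
|---|---|---|---|---|---|---|
| A: onset Day 60 grade 1, grade 3 on Day 95 | yes | yes | no | 3 | counted | absent |
| B: onset 5 days before first dose grade 1, grade 3 on Day 95 | yes | no | no | 3 | absent | absent |
| C: onset Day 90 grade 1, grade 3 on Day 95 | yes | no | yes | 3 | absent | counted |
| D: onset Day 90 at grade 3 | yes | no | yes | 3 | absent | counted |
| E: onset Day 60 grade 1, grade 3 on Day 70 | yes | yes | no | 3 | counted | absent |

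C, D and E are placed correctly. A is grade 1 throughout Period I but is shown there as grade 3. B counts in Tables 14.3.1.1 and 14.3.1.2.1 but in neither of the period tables. If a programmer instead dated the grade by when it was reached, A would be missing from both grade 3-4 tables, because Period II does not admit worsening.

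**Result with worsening added to Period II and the maximum taken within each period**

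- A: Period I grade 1, Period II grade 3.
- B: Period II grade 3.
- C, D, E: unchanged.

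**Size per patient.** With 20 planned per arm, 1/20 = 5 percentage points. For record A, if the patient has no other grade 3-4 TEAE, the Period 1 count is 1 instead of 0 and the Period 2 count is 0 instead of 1.

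**How many patients.** This cannot be computed. The documents give no rate of late worsening, and the visit schedule does not define who is at risk. The last dose is on Day 83 (Protocol 5.6.1) and adverse events are recorded for 4 weeks after the product is completed or discontinued (Protocol 7.4), which for a completer is Day 83 + 28 = Day 111. The end-of-study visit on Day 105 applies only to patients who stop early or do not enter study ABX464-302 (Protocol 5.2.5); those who enter it start open-label drug on Day 84 (Protocol 5.6.1).

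**The case against.** The strongest reply is that assigning an event to the period of its onset and showing its worst grade is a coherent, deterministic rule. That would hold if the plan used it throughout, but Period I is not an onset rule: it also admits worsening. An event recorded before dosing that worsens on Day 50 is in Period I; the same event worsening first on Day 95 is in neither period, although the SAP calls both treatment-emergent.

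Several limits do stand.

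- A reader might infer that any event reaching grade 3 after Day 84 is misplaced. Records C and D show otherwise: only onset on or before Day 84 is affected.
- A reader might take record B as common. The introduction to Protocol section 7 collects only screening-procedure events before dosing, although Protocol 7.1 and 7.4 read more widely, from consent. A pre-existing condition that worsens can also be entered as a new event under Protocol 7.1, and would then have its onset in Period II. The route is narrow but not closed.
- A reader might infer a threat to the primary comparison. The any-TEAE test (Table 14.3.1.2.1) and the grade 3 or higher row of Table 14.3.1.1 are not split by period and do not change. Listings show severity as reported.
- Dated severity changes cannot be assumed. Both SAP 10.1 and SAP 11.6.1 are conditional on this, and Protocol 7.5 asks for onset, resolution and severity but no date of change. If one record carries only the worst grade, record A still goes to Period I at grade 3. If a site enters the worsening as a new event, it goes to Period II. The same clinical course can thus be tabulated differently by data-entry practice.
- The cut is calendar Day 84, not last dose, so a patient who stops early has off-drug time in Period I. The documents do not state that the split separates on-drug from off-drug time, and the correction would not make it do so.
- Once worsening is admitted to Period II, one event can appear in both period tables, so these may sum to more than the overall count. This must be squared with the count-once rule.

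**Conclusion.** The point holds in a limited form. As written, an event with onset on or before Day 84 that first reaches grade 3 after Day 84 is tabulated in the Period 1 grade 3-4 table and cannot enter the Period 2 table. More rarely, an event recorded before dosing that first worsens after Day 84 is a TEAE in neither period table. The cause is a stated rule that conflicts with the SAP's own TEAE definition, not merely missing detail.

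Only the descriptive by-period tables are affected. Each such patient can shift a 20-patient arm by 5 points in the grade 3-4 pair, if that patient has no other qualifying event in the period concerned. The number of such patients is unknown and probably small. The conclusion assumes that the rules are applied literally and that the worsening is kept under the same AE number, either as a separate severity record or as a single record with the worst grade. Priority: minor.

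**What to change.** 1. In SAP 11.6.1, define Period II to include events that worsen after Day 84 as well as those that start then. Make the same change in Protocol 8.4, or list it in SAP 1.2.
2. Confirm whether the eCRF holds dated severity changes. Where it does, use the maximum grade reached within each period for the by-period tables, and keep the overall maximum for the all-period tables.
3. State that the count-once rule for severity changes applies within each table.
4. Footnote the by-period tables: one event may appear in both, so they need not sum to the overall count.

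The cost is a few sentences and, where dated changes exist, a small programming change. SAP 1.1 says that recruitment was still under way, and Protocol section 8 allows documented SAP amendments before final database lock. If the eCRF does not date severity changes, step 2 cannot be programmed and the SAP should say so.
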